- A description of the subject selection criteria and rationale for selection in terms of the scientific objectives and proposed study design;
- A compelling rationale for proposed exclusion of any sex/gender or racial/ethnic group;
- Justification for the inclusion of vulnerable groups such as children, prisoners, adults with impaired consent capacity, or others who may be vulnerable to coercion or undue influence.

Please consider these resources:

[NIH Diversity Policy](#)

[FDA Diversity Guidance](#) ⓘ

Pilot study

Inclusion criteria. Potential participants will be healthy controls who are employed in and around [name]. For inclusion in the pilot, they need to be 1) 18-55 years of age; 2) male or female gender 3) Able to read, understand and communicate in English; 4) Can have a past/current history of smoking.

Exclusion criteria. Intoxication with substances on day of the study.

Study Proper

Inclusion criteria. Potential participants will be: 1) Patients enrolled in the Bluegrass Clinic; 2) 18-55 years of age; 3) male or female gender 4) Able to read, understand and communicate in English; 5) willing to adhere to the general rules of the Bluegrass Clinic/SMARTClinic/Beyond Birth Clinic; 6) willing and able to abstain from drug use other than Suboxone; 7) exhaled breath on day of study CO < 5 ppm; 8) Stabilized on maintenance buprenorphine if having comorbid opioid use disorder.

Exclusion criteria. Traumatic brain injury, history of seizure disorder, history of or current diagnosis of schizophrenia, intracranial metal shrapnel, previous adverse effect with TMS, sub-threshold consistency while performing behavioral tasks, failure to show baseline attentional bias to smoking versus neutral cues.

We will exclude pregnant females in our study due to danger of MRI radiation to the unborn fetus.

The main study is not connected to the Bluegrass HIV clinic, SMART clinic or the Beyond Birth Clinic. A person can be enrolled and receiving care at these clinics, and their participation in the research project does not impact their standing in any of these clinics. Participation is truly voluntary in nature.

Attachments

Indicate the targeted/planned enrollment of the following members of minority groups and their subpopulations. Possible demographic sources: [Census Regional Analyst Edition](#), [Kentucky Race/Ethnic Table](#), [Kentucky Population Data](#).

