A sequential timeline of assessments and interventions are shown in table one. After informed consent, subjects will get an MRI brain scan at the Magnetic Resonance Imaging and Spectroscopy Center (MRISC) affiliated with University of Kentucky. Subjects will also be escorted to the MRISC at the UK Medical Center by the PI ([name]) and a research assistant. Subsequently, neuroimaging data (MRI brain) will be acquired using a Siemens 3-Tesla (3T) PRISMA MRI scanner as described under Data Collection below. This will happen on day 1. Then, on days 2 and 3, subjects will be scheduled for three hour experimental sessions at the TMS Suite at [name]. During these three hour sessions, subjects will perform the tobacco craving questionnaire (TCQ) while performing stress induced craving paradigm, attentional bias task and delayed discounting task. These activities will last an hour. Then we will obtain active motor threshold (AMT) from the first dorsal interosseous (FDI) muscle and left motor cortex, following which we will administer either a session of theta burst stimulation (TBS) for 9 minutes at 80% active motor threshold (AMT) or sham TMS to the left dorsolateral prefrontal cortex using a figure 8 coil and MagVenture MagPro x100 device (MagVenture A/S, Denmark), with TMS coil position stabilized using BrainSight (Rogue Solutions, Montreal, Canada). We will record motor evoked potential before and after the TBS session to assess response (10% increase in MEP to be a cutoff parameter). These activities will last another hour. After the TBS/sham TMS session, subjects will perform TCQ concomitant with the stress induced craving paradigm, attentional bias and delayed discounting tasks. These will last an hour. Then subjects will be transported to MRISC for their post TBS session MRI brain scan in the 3-Tesla (3T) PRISMA scanner.

Table 1

Study Task Study Day Pre- TBS Post-TBS

Urine Pregnancy Test 1

MRI brain at MRISC (Pre-TBS) 1

Exhaled CO 2 and 3 X

Motor Threshold 2 and 3 X

Eye tracking to measure AB 2 and 3 X X

Delayed Discounting Task 2 and 3 X X

Tobacco Craving Questionnaire 2 and 3 X X

TMS Side Effects Questionnaire 2 and 3 X

Treatment Acceptability Questionnaire 2 and 3 X

MRI brain at MRISC (Post-TBS) 2 and 3 X

Attachments

Subject Recruitment Methods & Advertising

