Following informed consent, the subject will be asked to come to MRISC for a MRI brain scan contingent on the investigative team obtaining a slot for this. The PI will coordinate with staff at MRISC to obtain a MRI slot. Subjects will also be escorted to the MRISC at the UK Medical Center by the PI ([name]) and a research assistant. Neuroimaging data (MRI brain) will be acquired using a Siemens 3-Tesla (3T) PRISMA scanner as described under Data Collection below. This will happen on day 1 and will last an hour. Then, on days 2 and 3, subjects will be scheduled for three hour experimental sessions at the TMS Suite at [name]. During these three hour sessions, subjects will perform the tobacco craving questionnaire (TCQ) while performing stress induced craving paradigm, attentional bias task and delayed discounting task. These activities will last an hour. Then we will obtain active motor threshold (AMT) from the first dorsal interosseous (FDI) muscle and left motor cortex, following which we will administer either a session of theta burst stimulation (TBS) for 9 minutes at 80% active motor threshold (AMT) or sham TMS to the left dorsolateral prefrontal cortex using a figure 8 coil and MagVenture MagPro x100 device (MagVenture A/S, Denmark), with TMS coil position stabilized using BrainSight (Rogue Solutions, Montreal, Canada). We will record motor evoked potential before and after the TBS session to assess response (10% increase in MEP to be a cutoff parameter). These activities will last another hour. After the TBS/sham TMS session, subjects will perform TCQ concomitant with the stress induced craving paradigm, attentional bias and delayed discounting tasks. These will last an hour. Then subjects will be transported to MRISC for their post TBS session MRI brain scan in the 3-Tesla (3T) PRISMA scanner.

Motor Threshold

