The pathophysiology of nicotine dependence includes the interaction between stress, environment and body physiology. Multiple previous studies have modeled craving for nicotine in the presence of stress, to approximate real world scenarios. Before we test TBS as a clinical intervention, we will explore whether one session of TBS can modulate craving in the context of induced stress. Two promising paradigms for stress induction are the cold pressor test (CPT) wherein participants immerse their feet in ice cold water (2-4 degree Celsius) for three minutes and the paced serial addition task (PASAT). The cold pressor test invokes an immediate cardiovascular stress response, initiated by the sympathetic nervous system, followed by a neuroendocrine response controlled by the hypothalamus-pituitary-adrenal (HPA) axis. The PASAT is a cognitively challenging task and will be performed in parallel with the CPT as an additional means for stress induction. The task requires participants to listen to a standardized audio-recording of a series of single-digit numbers and to say aloud the sum of the last two numbers presented (within each inter-trial interval). The PASAT will also last about three minutes. Peak stress response occurred 20 minutes after these paradigms were performed. In our pilot study, these paradigms will be performed simultaneously, and followed by the tobacco craving questionnaire (TCQ).

The Tobacco Craving Questionnaire-short form (TCQ-SF)

It consists of 12 items rated on a visual analogue scale. The original Tobacco Craving Questionnaire (TCQ) is a valid and reliable 47-item self-report instrument that assesses tobacco craving in four dimensions: emotionality, expectancy, compulsivity, and purposefulness. The short form has been found to be as valid and reliable as the original version.

Attentional Bias task

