For the pilot study, personal information collected (age, smoking history) will be stored in an excel sheet on a protected laptop at [name] (In a locked office and behind a protected firewall). No medical records will be reviewed for the pilot study. The excel sheets containing the personal information will be saved as an encrypted file every time, and will be stored separately from deidentified data and any other research data. Any data sharing will be restricted to the de-identified data. Data will be kept for a minimum of 7 years, and electronically destroyed by UK Policy A13-050 and UK Policy A05-055.

Study proper - Personal information of participants (Subjects' age, comorbid medical or psychiatric illnesses, history of substance use, history of traumatic brain injury/loss of consciousness, previous adverse effects with TMS, medication history, duration of treatment with suboxone, urine drug screens, breathalyzer test results) will be stored in an excel sheet on a protected laptop at [name] (In a locked office and behind a protected firewall). The excel sheets containing the personal information will be saved as an encrypted file every time. A data crosswalk of patient/participant name and MRN will be stored separately from deidentified data and any other research data. Any data sharing will be restricted to the de-identified data. Data will be kept for a minimum of 7 years, and electronically destroyed by UK Policy A13-050 and UK Policy A05-055. For the study proper, urine samples will be collected prior to every TMS session to perform drug screening.

For the pilot study, personal information of participants (age smoking history if any) will be stored in an excel sheet on a protected laptop at [name] (In a locked office and behind a protected firewall). A data crosswalk of patient/participant name and MRN will be stored separately from the deidentified data. The excel sheet containing personal information will be saved as an encrypted file every time new data is entered. Any data sharing will be restricted to the de-identified data. Data will be kept for a minimum of 7 years, and electronically destroyed by UK Policy A13-050 and UK Policy A05-055.

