For the main study, personal information of participants (Age, diagnoses of seizure disorder and schizophrenia if any, history of traumatic brain injury/loss of consciousness, medication history, duration of treatment with suboxone) will be stored in an excel sheet on a protected laptop at [name] (In a locked office and behind a protected firewall). The excel sheet containing personal information will be saved as an encrypted file every time new data is entered. A data crosswalk of patient/participant name and MRN will be stored separately from the deidentified data. Any data sharing will be restricted to the de-identified data. Data will be kept for a minimum of 7 years, and electronically destroyed by UK Policy A13-050 and UK Policy A05-055. Urine samples will be collected prior to every TMS session to perform drug screening.

Before recruitment of a subject into the study we will screen the chart for seizure disorder diagnoses and schizophrenia. We will also screen for previous adverse effects to TMS. Prior to the MRI session, we will also screen for metallic implants/devices in the body. This will also be clarified with the subject.

Should a participant voice suicidal ideation at any point during the study, a thorough risk assessment would be completed immediately

and the appropriate resources would be contacted including emergency and/or outpatient resources. To mitigate confidentiality or invasion of privacy, all procedures as part of the study will be completed at [name] offices. Participant personal information and medical/psychiatric history will be stored on the University of Kentucky building at [name]. Also, in order to mitigate risk of breach of confidentiality or invasion of privacy, HIPAA will be discussed with each participant at each session.

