The main risks with TMS include seizures. We will screen subjects for known risk factors for seizure with rTMS (medical screening and medical history). Personnel who administer rTMS are trained to recognize a potential seizure event and to act as "first responders" to administer appropriate initial care. All study personnel will undergo basic life skills (BLS) training, and seizure-specific training. The major physical signs the study personnel will look out for in detecting a potential seizure include chewing movements, convulsions/tremor/shaking, difficulty talking, a blank stare, eyes rolling up, and profuse sweating. If any of these signs are observed, study personnel will stop the research procedure and inquire whether the subject feels okay. If the subject is unresponsive (and therefore likely experiencing a seizure), first-aid will be supplied. The first-aid response consists of making sure the subject is physically safe for the duration of the seizure. This involves moving the subjects out of the TMS chair and onto the floor lying down on his or her left side. The subject will be kept lying down on his or her left side, while the staff call emergency medical help, via a 911 call. Resources available in the laboratory include a first-aid kit and immediate phone access. A seizure constitutes a reportable adverse event, and will thus be immediately reported to the IRB via the Safety Events Form mechanism.

Initial measures for syncope are identical to those for seizures. TMS will be terminated immediately, and the subject assisted in controlled reclining without impact. Airway breathing and circulation will be assessed. Unless tonic-clonic seizure activity occurs, the subject will be turned on one side to help clear the airway and avoid aspiration.

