An MRI procedure is considered to be "minimal risk" according to federal definitions. To date, no after effects have been revealed and the FDA has classified the MR procedure as possessing a "non significant risk" for the subject of study. To minimize risks, all subjects will be screened for metallic devices, implants and other contraindications to scanning. Women of child-bearing capacity will be evaluated for pregnancy using a urine pregnancy test prior to scanning. Those unlikely to tolerate the sense of confinement during scanning will also be excluded. Adequate safety monitoring and observation during scanning will be provided, as will measures to enhance the subject's physical and emotional comfort during the scan. It is possible that some subjects might experience minor distress by the confined and noisy conditions in the scanner. This possibility will be minimized by earplugs and headphones, and experienced technicians who will monitor all subjects for distress. In the event that a subject becomes anxious during a scan, the study will be halted. Subjects will be able to communicate with the investigators at all times using the intercom system should they wish to request that a study be terminated or have concerns or questions during the procedure. The subject is in full view of the operator at all times. The probability of an incidental finding that might lead to the diagnosis of an unknown abnormality is greater than zero. All subjects will be alerted to this possibility during the consent process. In that event, subjects or their designated physician will be provided copies of their anatomical scans and advised to seek further evaluation if they have concerns. Subjects will be transported between [name] and MRISC using UberHealth (www.uberhealth.com) operated and maintained by Department of Psychiatry.

Subjects will be transported between [name] and MRISC using UberHealth. The risk associated with transportation do not exceed any risk associated with vehicle transportation in everyday life.

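### No visible eligibility or screening rule covers known cardiovascular disease or uncontrolled hypertension before an ice-water stressor given up to four times per subject

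*Combined protocol and SAP*

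**What the plan says.** The stressor is described in the combined protocol and SAP under Research Procedures, Stress induced craving paradigm. Subjects put their feet in water at 2-4 °C for three minutes while doing a paced addition task. The stated mechanism is: "The cold pressor test invokes an immediate cardiovascular stress response, initiated by the sympathetic nervous system".

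Study Design and Research Procedures both pair the stressor with the craving questionnaire before stimulation and again afterwards: "After the TBS/sham TMS session, subjects will perform TCQ concomitant with the stress induced craving paradigm". Table 1 has no row for the stressor. It is scheduled through the questionnaire row, marked both pre and post: "Tobacco Craving Questionnaire 2 and 3 X X".

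The visible text on who may take part is spread over several sections:
- **Study Proper exclusions (subject selection text):** "Exclusion criteria. Traumatic brain injury, history of seizure disorder, history of or current diagnosis of schizophrenia, intracranial metal shrapnel, previous adverse effect with TMS", followed by two task-performance items and pregnancy.
- **Chart screen (Records, Privacy, and Confidentiality):** "Before recruitment of a subject into the study we will screen the chart for seizure disorder diagnoses and schizophrenia". Earlier bad reactions to TMS are added, and metal is checked before the scan.
- **Medical screen (same section):** "We will screen subjects for known risk factors for seizure with rTMS (medical screening and medical history".
- **Scan screen (same section):** metal, implants, other scan contraindications and pregnancy; also "Those unlikely to tolerate the sense of confinement during scanning will also be excluded".

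The same section lists what is recorded for each study-proper subject, including "comorbid medical or psychiatric illnesses, history of substance use" and medication history.

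**The concern.** The plan names a cardiovascular effect of the stressor, and nothing in the visible text decides who should be spared it. Exclusions specific to a procedure are written for stimulation (seizure history, shrapnel, cochlear implants) and for the scan (metal, pregnancy, confinement). The visible risk text covers stimulation, scanning and even the car journey between sites, but not the ice water.

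The population makes this relevant. The opening background paragraph associates smoking among people with HIV with cardiovascular illness, and the study proper is aimed at smokers. On the visible lists alone, a subject aged 18-55 with known heart disease or uncontrolled hypertension would not be screened out, unless another rule happened to catch them, such as a cardiac implant at the scan screen. Staff might have the diagnosis on record, but no visible instruction tells them to withhold the immersion.

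What is at stake is subject safety. No estimand, endpoint or analysis is affected.

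**Working it through.** The plan gives no figure on this point to reproduce. The check is an exposure count followed by a comparison of the screening texts.

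**Which study the stressor belongs to.** The stressor section speaks of a pilot study, but the background uses that word for the stimulation trial too. The healthy-control pilot is described as breath tests and the attentional bias task only. Study Design and Research Procedures place the stressor in the study proper.

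**Exposure per subject.** Inputs: 2 stimulation days (Days 2 and 3); 1 immersion before and 1 after stimulation on each day; 3 minutes each.
- Both days completed: 2 × (1 + 1) = 4 immersions; 4 × 3 = 12 minutes.
- One session only (subjects treated before the change to two sessions who do not return): 1 × (1 + 1) = 2 immersions; 2 × 3 = 6 minutes.

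**Exposure in the study.**
- Planned study-proper size of 30: 30 × 4 = 120 immersions at most.
- Continuation review: the stated total is 10, but the entries beside it are 9 previous and 0 new. The ceiling is therefore 10 × 4 = 40, or 9 × 4 = 36. It is lower if any of those counted were pilot subjects or had one session only.

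**Does any visible rule cover cardiovascular disease or blood pressure?**
- Study Proper exclusions: neurological, psychiatric, metal, TMS history, task performance, pregnancy. No.
- Subject Recruitment Methods (checks at the consent step): scan screening, urine drug screen, breathalyzer. No.
- Potential Risks & Benefits: cochlear implants and pregnancy. No.
- Chart screen: seizure disorder, schizophrenia, earlier bad reaction to TMS. No.
- Medical screen: directed at seizure risk. No.
- Scan screen: might catch an implanted cardiac device, but not hypertension or coronary disease.

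**Do the general safeguards fill the gap?** Data and Safety Monitoring promises prompt detection of harm. The PI-sponsored research section promises evaluation of unanticipated adverse events. Syncope is discussed in relation to TMS, and staff have life-support training. All of these act once harm has appeared; none decides who is immersed.

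**How many subjects might be affected?** The documents give no rate of cardiovascular disease or hypertension. As an illustration only, assume 5% to 20%:
- Of 30: 30 × 0.05 = 1.5 to 30 × 0.20 = 6 subjects; × 4 = 6 to 24 immersions.
- Of 10: 10 × 0.05 = 0.5 to 10 × 0.20 = 2 subjects; × 4 = 2 to 8 immersions.

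These figures count exposure. No probability of harm follows from them, and the point does not depend on the assumed range.

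**The case against.** The strongest reply is that the files most likely to hold such a rule cannot be seen. The application attaches a pre-screen form, a phone script used to judge suitability, a consent form, protocol files and a document on the stress paradigms themselves. If one of them screens for heart disease, the remaining work is to copy the rule across. This objection stands, and it limits the point to the visible text.

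A reader might infer that the study has no cardiovascular screen at all. The documents do not support that. Besides the attachments, eligibility rules are visibly scattered: cochlear implants appear only in the risk text and confinement only in the privacy section. Silence in the main exclusion list is therefore weak evidence of a missing rule.

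A reader might also infer that the plan admits the stressor is unsafe for some subjects. It does not. It describes the intended physiological effect and gives no contraindication, event rate or size of blood-pressure change. The step from that mechanism to withholding the immersion is clinical judgement.

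Nor can it be inferred that the laboratory lacks a blood-pressure cuff. The only recorder named is in the MRI suite, but part of the Resources section is not in the available text.

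Finally, the age limit of 55 lowers the risk, enrolment was about 10, and the file is stamped closed. These facts reduce the importance of the point. They do not supply the missing rule.

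**Conclusion.** The point holds in a limited form. In the visible application, no eligibility or screening rule addresses known cardiovascular disease or uncontrolled hypertension. Study-proper subjects nevertheless undergo a three-minute ice-water immersion up to four times (12 minutes in total), and the plan itself says it provokes a cardiovascular response. This is an omission, not a contradiction.

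The conclusion rests on three conditions: that the unseen attachments contain no such rule; that withholding the immersion from these subjects is sound clinical judgement; and that the study reopens or the stressor is used again. The first cannot be checked, so confidence is low to medium. The change is optional and worth considering because it is cheap and acts before exposure.

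**What to change.** Add known cardiovascular disease or uncontrolled hypertension to the Study Proper exclusions and to the pre-recruitment chart screen, at least as a bar to the immersion. Apply it from the comorbidity and medication history already recorded; the investigator sets the blood-pressure definition. State that an immersion stops on symptoms or at the subject's request. If the pre-screen form, phone script or stress-paradigm file already holds such a rule, copy it into the exclusion list.

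The cost is a few lines of text and a few items in a chart review already being done. The downside is that some subjects may become ineligible in a study already recruiting slowly (about 10 enrolled against an approved 60, pilot included). The documents give no rate; the assumed 5% to 20% would mean 1.5 to 6 of 30. Barring only the immersion would keep such subjects for the attentional bias and imaging aims, at the price of missing stress-induced craving data.

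A blood-pressure reading before the first immersion on each day is an optional extra. It adds a procedure and may need equipment, and the recommendation does not depend on it.
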